2.4 BASELINE EVALUATION

The following tests will be done after the patient is enrolled or re-enrolled in the study and within 28 days (except as indicated below) of initiating treatment with ruxolitinib. Tests do not need to be repeated if completed during screening and meet the timeframe for baseline evaluation.

- 2.4.1 Complete blood count (CBC) with differential, platelet count and reticulocyte count (within 2 weeks).
- 2.4.2 Acute Care Panel (sodium, potassium, chloride, CO₂, glucose, BUN, creatinine) and C-Reactive Protein (within 2 weeks).
- 2.4.3 Hepatic panel (alkaline phosphatase, ALT, AST, total and direct bilirubin), LDH, and mineral panel (serum calcium, phosphate, magnesium and albumin) (within 2 weeks).
- 2.4.4 Pretreatment assessment of circulating ATL cells present in the PBMC by Cellavision differential (see Sections [3.4.1.4](#) and [3.4.1.6](#), and [Table 4](#)) for T-cell receptor gamma (TCR γ) gene rearrangement to detect clonality (see Section [5.1](#)).
- 2.4.5 CMV serology and CMV antigens
- 2.4.6 FACS, Inflammatory marker and cytokine analysis
 - Baseline flow cytometry to assess lymphocyte sets and subsets (one 10-mL purple-top tubes; see Section [3.4.1.6](#) and [Table 4](#)) to be sent to Flow Cytometry/ Immunology

Laboratory Department of Laboratory Medicine for the Clinical Center. **NOTE:** In case of scheduling conflicts, TBNK may be substituted.

- 2.4.7 In vitro analysis of sensitivity to JAK inhibitors and other molecular therapeutics in 6-day proliferation assay (see Section [5.1.2](#))
- 2.4.8 Serum pregnancy test in women of childbearing potential within 3 days prior to starting the study drug.
- 2.4.9 **Optional Tumor Biopsy:** Patients with easily accessible tumor deposits who consent to this procedure will have a fine-needle aspiration or punch biopsy of one of their tumors for research (see Section [5.1.6](#)). These biopsies may be done by CT guidance.
- 2.4.10 Electrocardiogram
- 2.4.11 Bone marrow aspirate and biopsy will be obtained before treatment (biopsies performed at the Clinical Center within a year prior to treatment may be accepted at the discretion of the Principal Investigator).

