8. Radiographic restaging for response for patients with radiographically measurable or evaluable disease: CT scan neck, chest, abdomen and pelvis (or other imaging studies as appropriate) on pretreatment for all patients and then day 29 of cycles 1 and 2, and then every 2 cycles for patients who have radiographically measurable or evaluable disease.
9. Cellavision differential and FACS panel shown in **Table 4**, and Sections 3.4.1.6 and 3.4.1.4 for additional details. One 10 mL lavender top tube will be drawn for the FACS panel and sent to the Immunology Lab of the NIH Clinical Center 10/2C410. TBNK can be substituted for scheduling conflicts.
10. HIV and Hepatitis C testing only during screening. Hepatitis B testing as indicated also at screening; patients who have an indolent chronic Hepatitis B infection will have repeat serial Hepatitis B Quantitative DNA and serology every 2 cycles during treatment; this testing may be extended to every 3rd or 4th cycle at the discretion of the investigator after year 1 if the timing for other assessments is adjusted.
11. Patients who are complete responders by FACS evaluation of circulating ATL cells and/or radiographic assessment may have a second BM biopsy (optional) to confirm their response.
12. Samples to assess for IL-2R α IL-18 and TNF α will be drawn in 5mL SST tubes at pre-treatment, on day 15 (if feasible), pre-cycle 2 and 3, at the same time as disease restaging occurs, and at the end of treatment off study visits for all patients. Samples will be held at room temperature until picked up by a Lymphoid Malignancies Branch clinical researcher who will ship the samples to a Contractor for performance of the assays. Serum samples will also be routed by the Department of Laboratory Medicine to Mayo Laboratories for CLIA-certified analysis of soluble IL-2R α levels. See Section 5.1.3 for additional details.
13. In vitro (PBMC) proliferation assays will be an optional test for all patients to potentially be performed pre- and post-treatment on cycle 1 day 1, 15 and 29 and at the time of any subsequent follow-up visit at the PI’s discretion. Up to 50 mL of whole blood will be drawn in a heparinized (green top) tubes. **NOTE:** These assays will not be performed if the absolute lymphocyte count indicates an insufficient number of cells to form these assays at these time points.

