5.1.2 In Vitro Proliferative Assays

NOTE: These samples are optional and will be collected at the discretion of the PI. When collected, the following applies:

Samples for in vitro proliferative assays (PBMCs) will be drawn in a heparinized (green top) tubes (50 mL). The assays will not be performed if the absolute lymphocyte count indicates an insufficient number of cells to perform these assays at these time points. **If there is an insufficient number of circulating cells at these time points, the medical record will indicate this assessment was not performed due to insufficient material and will not be considered a protocol deviation.** Lymphoid Malignancies Branch Clinical Research personnel will pick up these tubes from phlebotomy.

These concentrations of the JAK inhibitors is based on the human pharmacokinetic data to represent a low but achievable *in vivo* drug level and a higher inhibitory level that cannot safely be achieved in patients to assess the drugs' potential inhibitory properties. The effect on proliferation will be assessed by addition of 3 H-thymidine 6 hours before the end of the 6-day cultures. Culture supernatants will be assessed by specific ELISAs for IL-2, IL-9, IL- 15 and IL-21.

These specimens may also be used to perform additional exploratory molecular analyses limited to immune response genes or genes known to be critical to the pathophysiology of HTLV-1 related ATL including but not limited to JAK1, JAK2, JAK3, IRF4, CCR4, NOTCH1 and p53.

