Updated Study Design (Amendment D): Although there were 4 responding patients in the first 12 patient who were treated, the activity was not sustained even in these patients; therefore, we are now changing the treatment regimen to evaluate the activity of augmented dosing (effective with Amendment D). We plan to treat a total of 9 patients at the MTD or MAD and will not proceed with the same original two-stage phase 2 dosing. Patients who discontinue treatment within the first 28 days for reasons other than toxicity will be considered inevaluable. In order to allow for this assessment of patients attempting higher treatment doses, the protocol will require an additional 15-21 patients. Accounting for the previously enrolled 12 subjects, the new design, and to assess up to 9 patients for response at the MTD/MAD level with the new increased dose levels as well as allowing for up to two (2) inevaluable patients: the new accrual ceiling will be set at 35 patients.

The major objective of this study continues to be to determine the antitumor activity of ruxolitinib with regard to response rate and time to progression. Response rate will be based on the number of patients who achieve either a complete or partial response to therapy. Time to progression will be measured from the date of registration until documentation of disease progression..

An exploratory analysis will be performed in the two subgroups of patients defined by the inhibition of their pretreatment *in vitro* ATL cells proliferation by ruxolitinib treatment. The patients will be distinguished on the basis of the results of a 6-day *ex vivo* culture analyses performed on patient peripheral blood mononuclear cells prior to drug administration. One subgroup of patients will be defined as those who fulfill the following criteria: peripheral blood mononuclear cells proliferate *ex vivo* ($\geq 5,000$ CPM/1 μ C) in 6-day culture and their thymidine uptake must be reduced by 40% by the addition of 10 μ M ruxolitinib. The other group of patients would be all the remaining treated patients that do not fulfill these criteria. Since a limited number of patient samples have been assessed to date, it is not clear what percentage of smoldering or chronic stage ATL patients will fulfill the criteria for group 1.

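### The second exploratory subgroup in Section 8, read as written, counts treated patients who have no ex vivo result as not meeting the assay criteria

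*Combined protocol and SAP*

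**What the plan says.** Section 8 (Statistical Considerations) describes one exploratory analysis, in two subgroups. It gives the basis of the split first: "The patients will be distinguished on the basis of the results of a 6-day" ex vivo culture of blood mononuclear cells taken before dosing. Group 1 must meet two conditions: proliferation of at least 5,000 CPM, and a 40% reduction in thymidine uptake with 10 μM ruxolitinib. Group 2 is what is left: "The other group of patients would be all the remaining treated patients that do not fulfill these criteria". On how large group 1 will be, Section 8 says that "it is not clear what percentage of smoldering or chronic stage ATL patients will fulfill the criteria for group 1". It names no outcome, test or threshold for this comparison.

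Section 5.1.2 (In Vitro Proliferative Assays) governs the assay. It states: "These samples are optional and will be collected at the discretion of the PI". It adds: "The assays will not be performed if the absolute lymphocyte count indicates an insufficient number of cells". In that case "the medical record will indicate this assessment was not performed due to insufficient material", and the omission is not a protocol deviation. The Study Calendar (Section 3.5) marks the assay as optional at baseline, and footnote 13 agrees: "proliferation assays will be an optional test for all patients". These provisions cover how a missing assay is recorded. None says how a patient without a result is to be analysed.

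**The concern.** The aim is to see whether ex vivo sensitivity goes with clinical outcome. That requires a group known to be sensitive and a group known not to be. Defining the second group as everyone left over treats an unknown assay status as a negative one.

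Two distortions are possible. Untested patients whose cells were in fact sensitive pull the second group towards the first and shrink a real contrast. Untested patients who respond better or worse for unrelated reasons can produce a contrast where none exists. Low lymphocyte count is one of the stated reasons for omitting the assay, so being untested may well be related to the type of disease. In a small open-label trial, wording that sits uneasily with its own stated basis also leaves room to settle the grouping after responses are known.

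**Working it through.** **Figures in the plan.** Section 8 gives no sample size, error rate or effect size for this analysis, so there is no figure to reproduce.

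**Inputs, all assumed.**
- u: share of treated patients with no result, 10% to 60%.
- f: share of tested patients meeting both criteria, 50% in the main case and 30% to 70% for the range.
- s: share of untested patients who would have met the criteria.
- p1 and p2: response rates in sensitive and non-sensitive patients. Response is chosen here as the outcome because Section 8 names none.

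**Dilution.** As fractions of all treated patients, group 1 is f(1−u). Group 2 is (1−f)(1−u) tested patients plus u untested. If untested patients respond like tested patients of the same sensitivity, then

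fraction of the true contrast left = 1 − u·s / [(1−f)(1−u) + u].

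This does not depend on p1 or p2. For f = 50%, u = 40% and s = f, it is 1 − 0.20/0.70 = 71%. At f = 50%:

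| u | s = f (as sensitive as tested) | s = f/2 | s = 0 |
|---|---|---|---|
| 10% | 91% | 95% | 100% |
| 20% | 83% | 92% | 100% |
| 40% | 71% | 86% | 100% |
| 60% | 62.5% | 81% | 100% |

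On an assumed 40-point contrast (50% v 10%), the s = f column leaves 36, 33, 29 and 25 points. With s = f, f from 30% to 70% and u from 10% to 60%, between 96% and 42% is left.

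**Spurious contrast.** Let both tested groups respond at 30%, and untested patients at 10% or 50%. The shift is 0.20·u / [(1−f)(1−u) + u] in absolute size. At f = 50% this is about 4 points at u = 10%, 11 at u = 40% and 15 at u = 60%, in either direction.

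**Scale.** With an assumed 7 v 7 patients at 50% v 10%, the standard error of the difference is √(0.25/7 + 0.09/7) = 0.22, or 22 points. That exceeds every shift above at f = 50%.

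**Power, two-sided Fisher test at 0.05, exact enumeration.** Assume 20 treated patients: 7 meeting the criteria, 7 tested and not meeting, 6 untested; response 50% v 10%.
- Tested only, 7 v 7: 13%.
- Pooled, 7 v 13, untested responding at 30% (s = 50%): 22%.
- Pooled, 7 v 13, untested responding at 10% (s = 0): 44%.

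In the spurious case with the same numbers, the test rejects with probability 0.045 (untested at 10%) or 0.023 (untested at 50%).

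**The case against.** The strongest reply is that group 2 is already fully defined. It is a complement, and a patient with no result does not fulfil the criteria, so every treated patient has a place. That stands. A reader might infer that Section 8 leaves untested patients unassigned, but its wording does not support that. The criticism is of the rule, which departs from the paragraph's own basis of classification.

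A reader might also infer that the protocol contradicts itself on whether the assay is required. Section 2.4 opens with "The following tests will be done after the patient is enrolled or re-enrolled in the study", and item 2.4.7 lists the assay without calling it optional. But 2.4.7 refers to Section 5.1.2, which says that it is optional, and the calendar and footnote 13 agree. There is no conflict to resolve.

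Next, group 2 may be the right place for some untested patients. Section 1.6.1 reports that cells from acute and lymphomatous disease did not proliferate spontaneously, and Section 2.2.7 foresees patients with no circulating abnormal cells. This also stands, and it is why the case of patients untested at random should not be taken as the expected one. It does not justify pooling. Smoldering disease also has a lymphocyte count below 4 × 10⁹/L (Appendix B), yet Section 1.6.1 reports that cells from smoldering and chronic patients did proliferate and were inhibited. Omissions at the investigator's discretion could go either way.

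Finally, pooling gives higher nominal power. That is true, but the gain comes from patients whose assay status is unknown, so the comparison is no longer one between assay results.

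**Conclusion.** The point holds and is minor. As written, the second subgroup classes untested patients with those tested and found not to meet the criteria, and the protocol foresees untested patients. The effect ranges from nil, if no untested patient is sensitive, to a loss of more than a third of a true contrast at f = 50% and u = 60%, if untested patients are as often sensitive as tested ones. Which applies cannot be known from the documents: u, f, s, the response rates and the group sizes are all assumptions, and untested patients could even be sensitive more often than tested ones.

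At the assumed group sizes, sampling error exceeds the shifts shown at f = 50%, and a spurious difference would rarely reach nominal significance. No decision is attached to the analysis. It would be wrong to read this point as a threat to the maximum tolerated dose, the response rate or time to progression, because none of them uses the assay.

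**What to change.** Amend the exploratory paragraph of Section 8, before the analysis, to say two things:

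1. The comparison is restricted to treated patients with a valid pre-dose assay result, those meeting both criteria against those not meeting them. A culture below 5,000 CPM counts as tested and not meeting.
2. Treated patients without a valid result are listed separately, with their number and the reason (too few cells, not collected, or no valid result).

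The two-part criterion stays as it is, and no change to Section 2.4.7 is needed.

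The cost is two sentences and no new samples. Section 5.1.2 already has insufficient material noted in the medical record, so the added record-keeping is a reason for the other missing results. The price is a smaller comparison with lower nominal power. It should be reported descriptively, with counts for all three sets of patients.

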9 COLLABORATIVE AGREEMENTS

Not applicable.

10 HUMAN SUBJECTS PROTECTIONS

10.1 RATIONALE FOR SUBJECT SELECTION

Men and women age 18 years or older of all races and ethnic groups are eligible for this trial if they meet the eligibility criteria. If differences in outcome that correlate to gender, racial, or ethnic identity were noted, accrual may be expanded or additional studies may be performed to investigate those differences more fully. Because there is no significant preclinical information regarding the risk to a fetus or newborn infant, pregnant or breastfeeding women will be excluded from participation in this trial. Since ATL patients have an underlying defect in their immunity due to the chronic infection, T-cell dysfunction and are already at risk for opportunistic infections, patients with hepatitis B with evidence of end organ damage or dysfunction or active hepatitis C are not eligible for this trial.

10.2 PARTICIPATION OF CHILDREN

Individuals under the age of 18 years of age are not eligible to participate in this trial. The immune physiology of children and the potential toxicity in this population are felt to be sufficiently

different from those of adult patients that a separate protocol, dedicated to pediatric patients, appears warranted. Therefore, children may be the object of a separate protocol once toxicity and a dose range with biological activity are defined in adults.

10.3 PARTICIPATION OF SUBJECTS UNABLE TO GIVE CONSENT

Adults unable to give consent are excluded from enrolling in the protocol. However, re-consent may be necessary and there is a possibility, though unlikely, that subjects could become decisionally impaired. For this reason and because there is a prospect of direct benefit from research participation (Section **10.5**), all subjects will be offered the opportunity to fill in their wishes for research and care, and assign a substitute decision maker on the “NIH Advance Directive for Health Care and Medical Research Participation” form so that another person can make decisions about their medical care in the event that they become incapacitated or cognitively impaired during the course of the study. Note: The PI or AI will contact the NIH Ability to Consent Assessment Team (ACAT) for evaluation to assess ongoing capacity of the subjects and to identify an LAR, as needed. Please see section **10.5.1** for consent procedure.

10.4 EVALUATION OF BENEFITS AND RISKS/DISCOMFORTS

The discomforts of a 28-day or longer treatment with oral ruxolitinib are expected to be minimal. The primary risk to patients participating in this research study is from unexpected or unforeseen toxicity from ruxolitinib as an investigational agent for this indication. Patients will be carefully monitored for any adverse events and appropriate care provided.

10.4.1 Risks from Study Procedures

10.4.1.1 CT Scans

CT scans often use a contrast agent. There is a small risk of having a reaction to the contrast and most often include nausea, pain in the vein where the contrast is given, headache, metallic and/ or bitter taste in the mouth and a warm, flushing feeling. Rarely, some people have more severe allergic reactions to the contrast which may include skins rashes, shortness of breath, wheezing or low blood pressure.

10.4.1.2 Radiation Exposure

On this study, patients will receive up to eight (8) CT Scans (CT Scan of neck, chest, abdomen and pelvis) maximum in annual period. Participants will undergo up to three (3) optional CT guided biopsy. The procedures for performing the CT will follow clinical policies, no special procedures will apply to these assessments for research purposes.

The total radiation dose for research purposes will be approximately 12.8 rem. This amount is more than would be expected from everyday background radiation. Being exposed to excess radiation can increase the risk of cancer.

10.4.1.3 Optional Tumor Biopsy

The biopsy may cause pain, bruising, bleeding and infection. The risks associated with biopsies are pain and bleeding at the biopsy site. In order to minimize pain, local anesthesia will be used. Rarely, there is a risk of infection at the sampling site. CT guidance may be used in obtaining biopsies (see **10.4.1.2** for radiation risk).

10.4.1.4 Bone Marrow Aspiration

These procedures usually cause only brief discomfort at the site from which the biopsy is taken. Rarely, infection or bleeding may occur at the needle site. A numbing agent that can cause a stinging or burning sensation may be injected at the site of your bone marrow biopsy.

The biopsy needle will go through the skin into the bone and may produce a brief, sharp pain. As the bone marrow liquid is taken from the bone, there may be a brief, sharp pain. Since the inside of the bone cannot be numbed, this procedure may cause some discomfort, however not all patients experience discomfort. The possible side effects associated with a bone marrow biopsy include pain, bleeding, bruising, and infection, as well as a reaction to the numbing agent.

10.4.1.5 Blood Sampling

Side effects of blood draws include pain and bruising, lightheadedness, and rarely, fainting.

10.4.1.6 Electrocardiogram

Some skin irritation can occur where the ECG/EKG electrodes are placed. The test is completely painless, and generally takes less than a minute to perform.

10.5 CONSENT AND ASSENT PROCESS AND DOCUMENTATION

The informed consent document will be provided to the participant or consent designee(s) as applicable for review prior to consenting. A designated study investigator will carefully explain the procedures and tests involved in this study, and the associated risks, discomforts and benefits. In order to minimize potential coercion, as much time as is needed to review the document will be given, including an opportunity to discuss it with friends, family members and/or other advisors, and to ask questions of any designated study investigator. A signed informed consent document will be obtained prior to entry onto the study.

The initial consent process as well as re-consent, when required, may take place in person or remotely (e.g., via telephone or other NIH approved remote platforms) per discretion of the designated study investigator and with the agreement of the participant. Whether in person or remote, the privacy of the subject will be maintained. Consenting investigators (and participant, when in person) will be located in a private area (e.g., clinic consult room). When consent is conducted remotely, the participant will be informed of the private nature of the discussion and will be encouraged to relocate to a more private setting if needed.

10.5.1 Consent Process for Adults Who Lack Capacity to Consent to Research Participation
For participants addressed in section **10.3**, an LAR will be identified consistent with Policy 403 and informed consent obtained from the LAR, as described in Section **10.5**.

10.5.2 Request for Waiver of Consent for Screening Activities

Prior to the subject signing the consent for this study pre-screening activities listed in section **2.2.1** may be performed.

We request a waiver of consent for these activities as they involve only minimal risk to the subjects. A waiver will not adversely affect the rights and welfare of the subjects given that the activities are only intended to determine suitability for screening for participation in research protocols. These activities could not practicably be carried out without the waiver as central recruiting services, utilized in the NIH Clinical Center, perform pre-screening activities for multiple studies and obtaining consent for each one is beyond their resources. The subjects will be provided with additional pertinent information after participation as they will be informed whether or not they are eligible to sign a consent for additional screening.

